## 6. Sample Size Determination

Approximately 45 patients are planned in total:

- Patients will be taken from the cohort of patients who completed the main study SCGAM-01 in the USA and Canada. The theoretical maximum number of SCGAM-01 patients will be approximately 35 (the expected number in the main study).
- Approximately 10 de novo patients who are under other SCIG treatment, but did not participate in the main study SCGAM-01 are planned in Canada.

No further sample-size considerations apply.

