## 8. General Issues for Statistical Analysis

Descriptive summaries will be presented for each of the primary and secondary variables. In general, summaries will be completed for all patients overall and by age group as described in section 4.2.

Continuous, quantitative variable summaries will in general include the number of patients with non-missing values (N), mean, standard deviation, median, minimum and maximum, 1st and 3rd quartile.

Categorical, qualitative variable summaries will include the frequency and percentage of patients who are in the particular category. In general the denominator for the percentage calculation will be based upon the total number of patients in the analysis population unless otherwise specified.

Whenever appropriate, the analyses will be stratified according to the predefined age groups taken from the SCGAM-01 study (2 to <6 |  $\geq 6$  to <12 |  $\geq 12$  to <17 |  $\geq 17$  to  $\leq 75$ ).

Additionally, for primary and secondary endpoints, the following subgroups will be investigated:

- Male vs female subjects
- A different definition of age groups: 2 to < 12, 12 to < 17, 17 to 65, and > 65 years

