### 8.2. Withdrawals

Patients who withdraw from the study prematurely will be considered in all data presentations for which they contribute data; in particular for the analysis of annual rates they will be considered with their actual observation periods.

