### 8.4. Derived and Computed Variables

The following derived and computed variables have been initially identified as important for the analysis of the primary and secondary target variables. It is expected that additional variables will be

required. The SAP will not be amended for additional variables that are not related to the primary target or key secondary target variables. Any additional derived or computed variables will be identified and documented in the SAS programs that create the analysis files. If the SAP is not amended, further derivations related to primary and secondary target variables will be described in the CSR.

- **Age** will be derived according to the usual definition that a person is  $n$  years old until she or he has completed her or his  $(n+1)^{\text{th}}$  year of life, using the date of informed consent as the reference date. This is also the definition that will be applied for evaluation of the age related inclusion criteria, and the stratification into the four predefined age groups [Unit: years]
- **Body Mass Index:**  $\text{BMI} = (\text{Body weight}) / \text{Height}^2$  [Unit:  $\text{kg}/\text{m}^2$ ]
- The **octanorm treatment period** is defined as the period between the day of first treatment with study drug to the end of the observation period. This will usually be the termination visit.
- The **rate of serious bacterial infections** per year during regularly repeated treatment with *octanorm* will be calculated as  $r = (\text{Total number of serious bacterial infections occurring in the treatment period}) / (\text{Duration of treatment period})$  [Unit: 1/years]
- The **rate of other infections** will be derived using the same method

Calculation of the confidence intervals of these rates will account for intra-patient correlation in incidents following a compound Poisson process model.[1]

With  $C_i$  infections for the  $i^{\text{th}}$  patient, and  $C$  total infections, the adjusted 2-sided 98% CI is calculated by:

$$\left[ e^{\ln(r) - 2.33 \cdot \sqrt{\frac{\sum C_i^2}{C^2}}}; e^{\ln(r) + 2.33 \cdot \sqrt{\frac{\sum C_i^2}{C^2}}} \right]$$

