- The **rate of infusions with one or more temporally associated AEs** will be calculated for each patient as  $r = (\text{Number of infusions with one or more temporally associated AEs}) / (\text{Number of infusions started})$ . An AE is defined as a temporally associated if, and only if, the onset (or worsening) is either during an infusion of study medication or within 72 hours of the end of the infusion. [Unit: N/A]
- The **rate of absence from work or school** will be based on the assumption of 200 working/school days per year, i.e. the rate is to be calculated as  $R = (1/200) \cdot (\text{Number of days absent from work or school}) / (\text{Patient years on octanorm treatment})$  [Unit: 1/years]

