All absences from work or school will be listed with duration and reason for absence. The individual absence rates per person-year will calculated and summarized by descriptive statistics, including the two-sided 90% confidence interval, again calculated on basis of the compound Poisson process model.

All hospitalizations will be listed with duration and indication for the inpatient hospital stay. The individual hospitalizations days per person-year will calculated and summarized by descriptive statistics, including the two-sided 90% confidence interval, again calculated on basis of the compound Poisson process model.

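### For hospital days and absences, the SAP pairs a mean of individual annual rates with a 90% CI built around the pooled rate, so the two describe different quantities and can disagree when a patient with such days leaves early.

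*SAP*

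**What the plan says.** SAP section 10 treats two groups of outcomes differently.

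- **Infections.** The rate is pooled. Section 8.4 puts "Total number of serious bacterial infections occurring in the treatment period" over the duration of treatment, extends the method to other infections, and prints the interval around that rate, introduced by "the adjusted 2-sided 98% CI is calculated by". For all infections, section 10 uses the same model at 90%.
- **Hospital days and absences.** A rate is formed for each patient first. For hospital days: "The individual hospitalizations days per person-year will calculated and summarized by descriptive statistics, including the two-sided 90% confidence interval". For absences: "The individual absence rates per person-year will calculated and summarized by descriptive statistics, including the two-sided 90% confidence interval". Both sentences then refer back to the compound Poisson model for the interval.

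The descriptive set in SAP section 8 is "mean, standard deviation, median, minimum and maximum, 1st and 3rd quartile", and section 12.2 repeats that continuous summaries include mean and SD. On withdrawals, section 8.2 says "in particular for the analysis of annual rates they will be considered with their actual observation periods". No minimum exposure or weighting by exposure is given. Section 8.4 also has an absence formula: days absent divided by "Patient years on octanorm treatment" and multiplied by 1/200. It does not say whether this is per patient or pooled.

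**The concern.** A mean of individual rates and a pooled rate agree when everyone is followed for the same time. Here follow-up can run from weeks, for an early withdrawal, to about 4.5 years, and withdrawn patients are not replaced. A few hospital days over a very short observation time become a very large annual rate, and that rate counts as much in the mean as one observed for years. The pooled rate hardly moves.

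Followed as written, the table would show a mean of one kind beside an interval of another, and a reader would take the interval as the uncertainty of that mean. In a study of medium-to-long-term treatment, the mean could also overstate the burden of hospital stay or absence because of one short exposure. Protocol section 4.3.1 lists adverse events among the grounds for withdrawal, so early hospital stay and early exit could occur in the same patient.

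**Working it through.** **The plan's own figures.** The two-sided 98% normal multiplier is 2.326, which rounds to the 2.33 printed in SAP 8.4. Also 4.5 × 52 = 234, the stated maximum number of infusions.

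**Formulas.** With dᵢ days and tᵢ years for patient i:
- pooled rate r = Σdᵢ / Σtᵢ
- 90% CI = r × exp(±1.645 × √Σdᵢ² / Σdᵢ). This is the SAP 8.4 form with the 90% multiplier, which the SAP does not print, and with days as the counts.
- mean of individual rates = (1/N) Σ(dᵢ / tᵢ)

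**Inputs.** N = 45 follows SAP section 6: "Approximately 45 patients are planned in total". The documents give no hospitalisation, absence or withdrawal rates, so the rest is assumed: 44 patients followed 3 years, 11 of them with 6 hospital days each (66 days), plus one patient with a 4-day stay who leaves early.

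**Leaving at week 4.**
- Leaver's rate: 4 / (28/365.25) = 52.2 days per year
- Mean: the 44 others contribute 66/3 = 22, so (22 + 52.2)/45 = 1.65
- Pooled: 70 / (132 + 0.077) = 0.530
- SE of the log rate: √(11×36 + 16)/70 = 0.290
- 90% CI: 0.530 × exp(±1.645 × 0.290) = 0.33 to 0.85

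| Leaves at | Leaver's rate | Mean | Pooled (90% CI) | Mean / pooled | Mean inside CI? |
|---|---|---|---|---|---|
| Week 2 | 104.4 | 2.81 | 0.53 (0.33–0.85) | 5.3 | no |
| Week 4 | 52.2 | 1.65 | 0.53 (0.33–0.85) | 3.1 | no |
| Week 8 | 26.1 | 1.07 | 0.53 (0.33–0.85) | 2.0 | no |
| Week 12 | 17.4 | 0.88 | 0.53 (0.33–0.85) | 1.7 | no, narrowly |
| Week 26 | 8.0 | 0.67 | 0.53 (0.33–0.85) | 1.3 | yes |

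The mean re-enters the interval at about week 13: (22 + 16.05)/45 = 0.846 against an upper limit of 0.853. If the week-4 leaver had no hospital days, the mean is 22/45 = 0.49 and the pooled rate 66/132.08 = 0.50.

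**Other assumptions for hospital days (N = 45).**
- 4.5 years, four patients with 5 days each. If all complete, both estimates are 20/202.5 = 0.099. If one of the four leaves at week 4, the mean is (3×5/4.5 + 65.2)/45 = 1.52, about 15 times the pooled 0.101 (CI 0.044–0.230). The pooled rate has moved by about 2%. With departure at week 26 the mean is (3.33 + 10.03)/45 = 0.30, still outside.
- 2 years, eight patients with 5 days each, one leaving at week 4: mean about 1.8, roughly 4 times the pooled 0.45 (CI 0.25–0.81).
- No early withdrawal, follow-up spread over 2 to 4.5 years: mean 0.148, pooled 0.137 (CI 0.060–0.311). The two nearly agree.

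**Absences.** Assumed: half the patients absent at some time; one patient with 5 to 10 days absent who leaves at week 2 to 8; N = 35 to 45; 2 to 4.5 years. A common factor of 1/200 would cancel from the ratio.

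| Background days/year | Mean / pooled | Mean inside CI? |
|---|---|---|
| 0.5 | 3.2–7.9 | no |
| 1 | 2.2–4.5 | no |
| 2 | 1.6–2.8 | no |
| 5 | 1.2–1.7 | yes in the milder cases |

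**The case against.** The stakes are modest, and this stands. SAP section 10 rules out confirmatory efficacy analysis. Hospitalisation is not a listed endpoint in protocol 3.1.2 or SAP 3.2.2, and absences are listed only in the SAP. Median, quartiles and maximum appear beside the mean, and every stay and absence is listed individually, so an extreme rate would be visible.

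The large effect needs a particular patient: one who leaves within weeks and already had hospital or absence days. SCGAM-01 completers enter only after good tolerance of the product (protocol 4.1.1), which makes very early illness-driven exit less likely for about 35 of the 45. This limits how often the problem would arise, but does not remove the mismatch.

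The interval argument assumes that the section 8.4 formula is the one used, because the SAP writes out no 90% version for day counts. That is fair. If that formula is used, however, the pooled rate must be computed as its centre, and section 10 never says that it is the reported estimate.

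Finally, the patient-weighted mean is a legitimate description and SAP 12.2 requires means for continuous variables. This also stands: there is no need to suppress it.

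**Conclusion.** As written, the individual-rate summary and its 90% CI refer to different quantities for hospital days and absences. This follows from the text, given that the section 8.4 formula is the one meant. The numerical consequence is conditional. If a patient with such days leaves within about the first 12 weeks, the mean could be well above the pooled rate and outside the interval: 1.7 to 5.3 times in the 3-year example for departures at weeks 12 to 2. How fast this fades depends on follow-up and on how rare the days are. For absences it is mild once the background reaches about 5 days a year.

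A reader might infer that the reported means in this trial would be driven by early withdrawals. The documents do not support that: they give no withdrawal, hospitalisation or absence rates, and an early leaver without such days barely changes the mean. Nor does the point touch the infection rates, where estimate and interval share the pooled rate. It is a worthwhile correction to a descriptive output.

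**What to change.** In SAP section 10, make total days divided by total person-years the point estimate for hospital days and for absences, and attach the 90% CI to it, as is done for infections. Write out the 90% formula with days as the counts. Keep the individual-rate summary (mean, median, quartiles) as a supplementary description without that CI, and show observation time beside it. Reconcile the section 8.4 absence formula with section 10: state whether it is pooled or per patient, and whether the 1/200 factor applies to the reported rate.

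The cost is SAP wording and one extra line per table. No new data are needed, and the infection-rate method is reused.

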## 11. Safety and Tolerability Analyses

The safety analysis will comprise descriptive statistics, tabulations and listings of all TEAEs, safety laboratory results, viral markers, vital signs and physical examination findings.

### 11.1. Adverse Events

All reported AEs will be coded according to MedDRA.

An AE is defined as treatment-emergent, if first onset or worsening is during the *octanorm* treatment period. Only treatment-emergent AEs (TEAEs) are accounted for in the analysis.

For each TEAE, the time relative to the start of the infusion will be calculated and the TEAE will be classified as temporally associated if the onset is during the infusion or within 72 hours after the end of the infusion.

All reported events will be listed and tabulated in full detail, in particular the following key figures will be presented:

- Total number of TEAEs reported.
- Number of temporally associated TEAEs.
- Infusion rate at the onset of temporally associated TEAEs
- Narratives will be prepared describing each death, other SAEs, and other significant AEs that are judged to be of special interest because of clinical importance.

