
Safety Analysis Plan:
 
The safety analysis will comprise descriptive statistics, tabulations and listings of all TEAEs, safety laboratory results, vital signs and physical examination findings. All reported AEs will be coded according to MedDRA.
 
For this extension study, any AE is regarded as treatment-emergent if the patient migrated from the main to the extension study without being treated with another IgG product. If another product was used between the two studies, then an AE in the extension study is classified as treatment-emergent if onset or worsening is after start of the infusion of Octanorm at the screening visit. Only TEAEs are accounted for in the analysis.
 
For each TEAE, the time relative to the start of the infusion will be calculated and the TEAE will be classified as temporally associated if the onset is during the infusion or within 72 hours after the end of the infusion.
 
All reported events will be listed and tabulated in full detail, in particular the following key figures will be presented for each age group and for the study as a whole:
 
 • Total number of TEAEs reported. 	

Name of Sponsor/Company: OCTAPHARMA, Pharmazeutika Prod.Ges.m.b.H., [name]	
Name of Investigational Product: Octanorm	Protocol Identification Code: SCGAM-03
Name of Active Ingredient: Human Normal Immunoglobulin	Edition / Date of Protocol: October 04, 2018

• Number of temporally associated TEAEs.• Infusion rate at the onset of temporally associated TEAEs (frequencies and percentages).• Narratives will be prepared describing each death, other SAEs, and other significant AEs that are judged to be of special interest because of clinical importance. 
The QoL data will be presented descriptively by visit, along with the change from screening (defined as the first infusion).
	

FLOW CHART OF STUDY EVENTS

ASSESSMENTS	Screening – First visit (Week 65 of SCGAM-01)	Octanorm Treatment Visits					Termination (ET)
	---	---	Every 12 Wks ⁴ [every 24 wks]	---	Every 12 Wks ⁴ [every 24 wks]	---	---
WEEKS	1	12	24, 36, 48 [36]	60	72, 84, 94, 108, etc [84, 108, 132, etc]	Final Infusion Visit	One week after last infusion
Informed consent, In-/exclusion criteria ³	x						
Body weight ³	x	x	x	x	x	x	
Physical examination ³ , vital signs ¹	x	x	x	x	x	x	x
IgG trough levels ³	x	x	x	x	x	x	x

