#### 3.2. Study Endpoints (Target Variables)

##### 3.2.1. Primary Target Variables

There is no single primary endpoint in this present extension study. The primary objective is to assess safety and tolerability in medium-to-long-term administration, and this will be assessed by means of the following outcome variables:

- Occurrence of treatment-emergent AEs (TEAEs) throughout the entire treatment period starting with the first infusion of IMP.
- Occurrence of temporally associated TEAEs.
- TEAEs by speed of infusion.
- Local injection-site reactions.
- Vital signs (blood pressure, pulse, body temperature, respiratory rate).
- Physical examination.
- Laboratory parameters (haematology, clinical chemistry and tests for viral safety).

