#### **9.4. Measurement of Treatment Compliance**

The following parameters will be listed and summarized per patient and/or per infusion:

- Body weight
- Actual dose (total and per kg body weight, based on the latest available weight measurement)
- Total dose of *octanorm* administered
- Total number of infusions administered
- Total volume of solution administered
- Infusion times
- Overall amount of product administered (only included in data listings)
- Maximal volume administered (in total and per kg body weight)
- Infusion flow rates (overall and per site) (center visits only)
- Number of infusion parts administered per infusion (center visits only)
- Number of infusion lines used simultaneously (center visits only)

Deviations from the planned treatment schedule will be summarized by counting the number of infusions that deviate from the scheduled intervals by more than 2 days, and by listing all cases with more than two days deviation individually.

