### 11.2. Infusions with One or More Temporally Associated AEs

The number of infusions with at least one temporally associated adverse event (including AEs judged not to be related to *octanorm* by the investigator) over the total number of infusions will be calculated for each patient, and the ratio will be presented, including the associated upper one-sided 95% confidence limit. The calculation of this confidence interval will take into account the observed intra-patient correlation - this is necessary because each patient may experience more than one infusion with an associated AE; it can therefore not be assumed that the observed events are statistically independent.

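### The stated output for the primary variable on adverse events by infusion speed has no count of infusions at each rate and no rule for onsets after the infusion ends

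*SAP*

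**What the plan says.** SAP 3.2.1 lists "TEAEs by speed of infusion" among the variables that assess the primary objective, as does protocol 3.1.1. The matching output in SAP 11.1 is "Infusion rate at the onset of temporally associated TEAEs", and protocol 9.2.3.1 has the same item. The protocol synopsis extends it to "Infusion rate at the onset of temporally associated TEAEs (frequencies and percentages" but names no base for the percentages. An event is "classified as temporally associated if the onset is during the infusion or within 72 hours after the end of the infusion".

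Three other places come close:

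- SAP 11.2 takes infusions with at least one temporally associated event "over the total number of infusions will be calculated for each patient, and the ratio will be presented", with a one-sided confidence limit. It is not split by speed.
- SAP 9.4 includes "Total number of infusions administered" and a line on flow rates. The first is not broken down by rate. The second is limited to center visits and is not linked to adverse events.
- For adverse events as a whole, SAP 11.1 gives "Total number of TEAEs reported".

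SAP sections 2 and 14 defer the list of tables to a separate document.

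**The concern.** A variable named for events by speed asks whether events are more frequent when the product is infused faster. That needs two counts per rate: infusions with an event, and infusions given. The plan states only an event count by rate. If most infusions run at one rate, most events will be recorded at that rate whatever the risk per infusion.

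The second gap is one of definition. The temporal window runs 72 hours past the end of the infusion, and at such an onset nothing is being infused. One programmer might drop these events. Others might assign the last, maximum or mean rate. The tables could differ, and the plan does not say which is correct.

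**Working it through.** **1. The outputs side by side**

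| Place | What is counted | Base | By rate? |
|---|---|---|---|
| SAP 11.1, rate at onset | temporally associated TEAEs | not stated | yes |
| SAP 11.2 | infusions with at least one temporally associated event | all infusions | no |
| SAP 9.4, infusions | infusions | none needed | no |
| SAP 9.4, flow rates | flow rates at center visits | none needed | not counted by rate, not linked to events |
| SAP 11.1, total | all TEAEs | none | no |

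No row has both a per-infusion base and a split by rate.

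**2. Reach of the center-visit line**

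The plan's maximum of about 234 infusions reproduces: 4.5 years × 52 weeks = 234 weekly, or 117 bi-weekly. Protocol 5.4 puts infusions on site at Week 1, Week 12 and every 12 weeks after that. To Week 228 that is 1 + 19 = 20, or 21 with a separate final infusion visit.

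- Weekly: 20/234 = 8.5% to 21/234 = 9.0%.
- Bi-weekly: 20/117 = 17.1% to 21/117 = 17.9%.

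This is the coverage of that one summary line. It is not a measure of how much rate data exists.

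**3. What the missing denominator does**

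Assume 80 events at a high rate and 20 at a low rate over 1000 infusions, with each event on a different infusion. Let f be the share of infusions at the high rate.

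Ratio per infusion, high to low = [80/(1000f)] / [20/(1000(1−f))] = 4(1−f)/f

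| f | High | Low | Ratio |
|---|---|---|---|
| 50% | 80/500 = 0.16 | 20/500 = 0.04 | 4.0 |
| 80% | 80/800 = 0.10 | 20/200 = 0.10 | 1.0 |
| 95% | 80/950 = 0.084 | 20/50 = 0.40 | 0.21 |

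On an event base the stated output is the same in all three rows: 80% of events at the high rate and 20% at the low rate. The total of 1000 cancels, so only f matters.

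**4. Onsets after the infusion**

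SAP 11.1 calculates the time of each TEAE relative to the start of the infusion, so an event can be tied to an infusion. No section then gives it a rate. The documents do not say how many onsets to expect after the infusion, so the effect cannot be sized.

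**5. Overall TEAEs**

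Protocol 6.2.1 says infusion numbers vary with entry date, and SAP 4.1 allows up to about 4.5 years. Ten events (assumed) in one patient are 10/0.5 = 20 per patient-year over half a year, and 10/4.5 = 2.2 over the maximum. Total infusions (SAP 9.4) and the treatment period (SAP 8.4) are already planned, so both denominators are available.

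**The case against.** The strongest reply is that SAP 11.1 gives key figures within a fuller tabulation, that table detail is deferred, and that the study is descriptive. This stands as a reason to rate the point low. It does not supply the denominator, because neither the key figures nor the deferral mentions infusions by rate.

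It is also fair that SAP 9.4 puts no center-visit limit on volume or infusion times. If both are held per infusion, an average rate could be derived for home infusions. That helps feasibility, but no such derivation is planned.

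Four stronger readings are tempting, and the documents do not support them:

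- *The percentages will be of patients, so the more-used band will always look worse.* SAP 8 says "In general the denominator for the percentage calculation will be based upon the total number of patients in the analysis population unless otherwise specified", but only as a general default. The item is a property of each event, so events are the more natural base.
- *Most temporally associated events will lack a rate, because the 72 hours dominate the window.* That is a share of clock time. The documents give no distribution of onset times.
- *The rule will be chosen after the data are seen.* SAP 8.4 does allow further derivations for primary variables to be described in the study report. It also implies that the SAP may be amended for primary variables, and SAP 5.1 requires an approved final SAP before the final analyses. The rule is open, and nothing shows an intention to set it late.
- *The lack of an overall TEAE rate is an error.* SAP 11.2 already plans a per-infusion ratio for temporally associated events. In a single-arm descriptive study, an exposure-based rate for all TEAEs is a useful addition.

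**Conclusion.** The point holds as a minor, inexpensive improvement. A primary variable has a stated output that cannot answer the question in its name, and the attribution of post-infusion onsets is undefined. The possible size is shown by the ratio moving from 4.0 to 0.21 with an unchanged event table. That rests on assumed event counts and assumed shares of infusions, and illustrates the range rather than predicting this trial. The conclusion itself rests on the text: no section pairs events with infusions at the same rate, and none assigns a rate after the infusion ends. The practical effect is limited because no confirmatory analysis or stopping rule depends on this variable.

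**What to change.** Amend SAP 11.1 and 11.2 before database lock:

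- Keep the rate-at-onset output for onsets during the infusion.
- Add a table by pre-specified rate band: infusions with at least one temporally associated TEAE over all infusions in that band. Use one pre-specified rate per infusion for both numerator and denominator.
- Link each post-infusion onset to the preceding infusion, and show during-infusion and post-infusion onsets separately.
- Include home infusions where a rate is recorded or can be derived from volume and time, shown apart from site infusions. Otherwise limit the table to site infusions and say so.
- Label the table descriptive and not causal. Protocol 5.5 allows rate increases only after two well-tolerated administrations, so tolerant patients gather in higher bands. An infusion may also be slowed because of an event.
- As a secondary addition, report overall TEAEs per infusion and per patient-year.

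The cost is a few tables and a short text change, with no new data collection. Protocol 5.7.2 has speed in the diary and infusion details in the eCRF, and protocol 8.1.1 requires the rate to be verifiable from source. Protocol 6.1.2 transfers only relevant diary data, so home rates may be incomplete. If nearly all infusions fall in one band, the table will say little, and the report should state that.
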